1.1 Synopsis

Protocol Title:

Sponsor Study No.:

Phase: 2

Sponsor: Apnimed, Inc.

Rationale:

Apnimed is developing the combination of atomoxetine and oxybutynin for the treatment of obstructive sleep apnea (OSA). Initial Phase 2 studies of the combination were conducted with marketed oxybutynin (combination designated AD-036), which is a racemic mixture of R- and S-oxybutynin. Subsequent development is being pursued with R-oxybutynin (combination designated AD-109), a new enantiomerically pure form of oxybutynin which is proposed to have an improved safety and efficacy profile in OSA compared to racemic oxybutynin.

Previous studies of AD-036 provided dose-response efficacy and safety data across a broad spectrum of OSA disease severity. Study APC-004 is designed to extend and confirm these findings to AD-109 in a population with mild- to moderate OSA, in parallel with other studies of AD-109 planned by Apnimed in moderate- to severe OSA.

Overall Design:

Study APC-004 is a randomized, double blind, placebo-controlled, 3-period, single-dose crossover study in patients with mild- to moderate OSA. A screening visit and polysomnographic (PSG) exam will be conducted to establish that each participant meets study enrollment criteria. Each participant will then receive a single dose of each of the following during 3 overnight PSG exams, each separated by a one week washout period:

- Atomoxetine 75 mg + R-oxybutynin 2.5 mg (i.e. 75/2.5)
- Atomoxetine 37.5 mg + R-oxybutynin 2.5 mg (i.e. 37.5/2.5)
- Placebo

Primary efficacy and safety endpoints will compare the 75/2.5 and 37.5/2.5 doses to each other and to placebo.

Number of Participants:

A total of 30 participants will be enrolled.

Study Duration:

The overall study duration will be up to 12 weeks, as follows:

- Screening, up to 4 weeks;
- 3-period crossover, up to 6 weeks;
- End of Study Evaluation, 2 weeks post crossover period

1.2 Schedule of Activities (SoA)

Table 1Schedule of Activities

	Screening		3-Way Crossover Period					End of Study Evaluation	
Procedures	V1	V2	V3	Wash-out	V4	Wash-out	V5	Wash-out	Evaluation
Trial Day (Visit Window)	Up to 4 weeks		Up to 6 weeks					2 wks post $V5 \pm 3 d$	
Informed consent	X								
Non-PSG enrollment criteria ²	X								
Demography	X								
Physical exam	X								
Medical history	X								
Clinical laboratory testing	X								X
Pregnancy test ³	X								
12 Lead ECG	X								
PSG Exam		X ⁴	X		X		X		
Randomization ⁵			X						
HS study treatment ⁶			X		X		X		
DSST, KSS, Sleep quality VAS ⁷			X		X		X		
Vital signs ⁸	X	X	X		X		X		
AE/SAE monitoring			X	X	X	X	X	X	X
Prior/concomitant medication	X	X	X	X	X	X	X	X	X

6 January 2021 7 of 54 V2.0

¹ Each washout period is a minimum of 7 days

² Includes ESS, PGI-S, and history of OSA symptoms

³ WOCBP only

⁴ Only patients who meet all non-PSG enrollment criteria at Visit 1 are eligible for a screening PSG

⁵ Randomization occurs when participant meets enrollment criteria up to the time of the first crossover period.

⁶ Study medication administered immediately before lights out

⁷ Administer at similar time after awakening after each crossover PSG, approximately 1 hour after awakening

⁸ Vital signs include the following: seated blood pressure, pulse, respiratory rate; vital signs on PSG nights taken after admission to PSG lab.

Clinical Study Protocol CONFIDENTIAL

Abbreviations: AE = adverse event; DSST = Digit Symbol Substitution Test; ECG = electrocardiogram; ESS = Epworth sleepiness scale; KSS = Karolinska sleepiness scale; PGI-S = patient global impression of severity of OSA; PSG = polysomnography; SAE = serious adverse event; VAS = visual analog scale; WOCBP = women of childbearing potential.

6 January 2021 8 of 54 V2.0

2 Introduction

2.1 Study Rationale

Previous studies conducted by Apnimed (under IND 136752) and academic investigators support that the combination of atomoxetine and oxybutynin is safe and effective for the treatment of OSA. These initial Phase 2 studies of the combination were conducted with marketed oxybutynin (combination designated AD-036), which is a racemic mixture of R- and S-oxybutynin. Subsequent development (under IND 141505) is being pursued by Apnimed with R-oxybutynin (combination designated AD-109), a new enantiomerically pure form of oxybutynin which is proposed to have an improved safety and efficacy profile in OSA compared to racemic oxybutynin.

Previous studies of AD-036 provided dose-response efficacy and safety data across a range of doses. Doses of atomoxetine ranged between 25 mg and 80 mg, and doses of racemic oxybutynin between 1.5 and 5 mg. Combinations with the highest doses were clearly more effective than combinations with the lowest doses, with mid-range doses retaining substantial efficacy. All doses were safe and well-tolerated, with suggestion of positive correlation between dose and generally mild adverse effects. Study APC-004 is designed to extend and confirm these findings to AD-109, combining a dose of 2.5 mg R-oxybutynin with either 75 mg or 37.5 mg atomoxetine. Study APC-004 will enroll patients with mild- to moderate OSA, in parallel with other studies of AD-109 planned by Apnimed in moderate- to severe OSA.

2.2 Background

2.2.1 Obstructive Sleep Apnea

The National Commission on Sleep Disorders Research identified sleep disorders as a major public health burden. OSA is the most common and serious of these sleep disorders and affects approximately 20 million people in the United States (US), with approximately 13% of men and 6% of women affected (Peppard et al, 2013). OSA is characterized by repetitive collapse or 'obstruction' of the pharyngeal airway during sleep, manifesting as repetitive episodes of hypopnea (i.e., shallow breathing) or apnea (i.e., paused breathing). These episodes of hypopnea or apnea may lead to arousal from sleep, sleep fragmentation, excessive daytime sleepiness, and/or neuropsychological impairment.

Research has shown that a number of pathogenic factors, or traits, contribute to the development of OSA (Eckert et al, 2013; Wellman et al, 2011; Wellman et al, 2013; Younes, 2003). The most

important factors are the presence of an anatomically small, collapsible upper airway and a loss of pharyngeal muscle tone or responsiveness during sleep.

Long-term, OSA is associated with increased mortality and a number of adverse cardiovascular, neurocognitive, metabolic, and daytime functioning consequences (Somers et al, 1995; Nieto et al, 2000; Brooks et al, 1997; Peppard et al, 2000; Hung et al, 1990; Wessendorf et al, 2000; Hoffstein, 1994; Shahar et al, 2001; Redline et al, 1997; Findley et al, 1988).

2.2.2 Unmet Medical Need

Treatment for OSA changed little over the past 40 years, with the overwhelming majority of patients treated with positive airway pressure, the most common of which is continuous positive airway pressure (CPAP), provided by a machine that mechanically maintains an open airway. Other treatments, such as pharyngeal surgery, mandibular advancement devices, and implantable nerve stimulators, were developed to address the anatomical predisposition to collapse; however, they have shown limited efficacy for niche populations.

While CPAP and related therapies are effective in improving sleep characteristics and oxygenation, many, perhaps most, patients find these devices uncomfortable or intolerable, and most estimates indicate that fewer than 50% of patients prescribed CPAP use it more than 4 hours per night, if at all (Weaver and Sawyer, 2010). Efforts to develop pharmacologic therapies, such as antidepressants, stimulants, and hormonal agents, for the treatment of OSA have been ongoing for at least 20 years, with no success thus far.

As many patients cannot use CPAP because they find it intolerable, this represents a significant health concern, as OSA is associated with numerous co-morbidities and increased mortality. Alternative options, such as drugs that activate the pharyngeal muscles, are needed.

2.2.3 Biological Rationale

AD109 is a new fixed dose drug combination of atomoxetine and R-oxybutynin being developed for OSA. Atomoxetine is a pre-synaptic norepinephrine reuptake inhibitor indicated for the treatment of attention deficit hyperactivity disorder in children and adults. R-oxybutynin has never been marketed, but racemic oxybutynin is approved as an antispasmodic drug that inhibits the muscarinic action of acetylcholine on smooth muscle and is indicated for the treatment of symptoms of bladder instability associated with voiding in patients with uninhibited neurogenic or reflex neurogenic bladder such as urgency, frequency, urinary leakage, urge incontinence and dysuria.

Efficacy of oxybutynin in overactive bladder may result both from antimuscarinic effects of oxybutynin and smooth muscle spasmolytic effects. The contribution to efficacy of oxybutynin in OSA is believed to be related to antimuscarinic effects, whereas spasmolytic effects may lead to effects on the bladder that are undesirable in typical OSA patients. The R-enantiomer of oxybutynin has been shown to confer the antimuscarinic effect of oxybutynin, whereas the spasmolytic effects (and other effects on calcium channel antagonism and local anesthetic effects) are non-stereoselective properties of both the enantiomers. Apnimed therefore believes that the combination of the R-enantiomer of oxybutynin with atomoxetine may have an improved safety and efficacy profile in OSA compared to the combination with the racemate of oxybutynin.

3 Endpoints

	Endpoints
Primary	Change in Hypoxic Burden (HB) 4% (scored in reference to AHI 4%), 75/2.5 dose vs. placebo
Secondary	 Change in HB 4%, 37.5/2.5 dose vs. placebo and vs. 75.2.5 Change in Apnea Hypopnea Index (AHI) 4% Change in Oxygen Desaturation Index (ODI) Total time with SaO₂ <90%, PSG nights Proportion of participants with ≥50% reduction, AHI, HB and ODI
Exploratory	 Karolinska sleepiness scale Sleep Quality VAS AHI 3% (hypopnea scored when associated with 3% O₂ desaturation or arousal) OSA endotypes endpoints (Vpassive, Vactive, Muscle Compensation, Loop Gain) PSG sleep and arousal parameters
Safety Endpoints	 Physical exam, vital signs, clinical laboratory assessment Spontaneous adverse events, including the post-dosing period DSST PSG parameters: heart rate, ECG, EEG, oximetry

Abbreviations: AHI = apnea-hypopnea index; DSST = Digit Symbol Substitution Test; ECG = electrocardiogram; EEG = electrocardiogram; HB = hypoxic burden; ODI = Oxygen Desaturation Index; OSA = obstructive sleep apnea; PSG = polysomnography; $SaO_2 = oxygen saturation$.

4 Study Design

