8.1 Sample Size Determination

A total of 30 patients will enter the 3-treatment crossover study. The study will have 80% power to detect a treatment difference on the primary endpoint at a two-sided 0.05 significance level, if the true difference between treatments on HB is at least -3.7 %min/h. This assumes that the within-subject standard deviation is 9 and a discontinuation rate of less than 20%.

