1. INTRODUCTION

This statistical analysis plan (SAP) is based on the Protocol # APC-004 Version 2.0, dated 06 January 2021, titled “Phase 2 Randomized Double-Blind Placebo-Controlled 3-Period Single-Dose Crossover Study to Evaluate the Safety and Efficacy of Two Doses of AD-109 in Mild to Moderate Obstructive Sleep Apnea.” Apnimed is developing the combination of atomoxetine and oxybutynin for the treatment of obstructive sleep apnea (OSA). Initial Phase 2 studies of the combination were conducted with marketed oxybutynin (combination designated AD-036), which is a racemic mixture of R- and S-oxybutynin. Subsequent development is being pursued with R-oxybutynin (combination designated AD-109), a new enantiomerically pure form of oxybutynin which is proposed to have an improved safety and efficacy profile in OSA compared to racemic oxybutynin.

Previous studies of AD-036 provided dose-response efficacy and safety data across a broad spectrum of OSA disease severity. Study APC-004 is designed to extend and confirm these findings to AD-109 in a population with mild-to-moderate OSA, in parallel with other studies of AD-109 planned by Apnimed in moderate-to-severe OSA. Study APC-004 is a randomized, double blind, placebo-controlled, 3-period, single-dose crossover study in patients with mild-to-moderate OSA.

This document details the statistical methods planned to perform the final analyses of this study. The reader interested in detail on study rational, study design, and medical background is invited to refer to the study protocol.

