2.2. Endpoints

2.2.1. Primary Endpoint

The primary efficacy endpoint is change in \log_{10} of Hypoxic Burden (HB) 4% plus one (scored in reference to AHI[4%]), 75/2.5 dose vs. placebo

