4.5. Multiple Comparisons

Each endpoint for this study implicitly contains three hypothesis tests based on comparisons between study treatments: i) 75/2.5 dose vs placebo, ii) 37.5/2.5 dose vs placebo, iii) 37.5/2.5 dose vs 75/2.5 dose. The sequential testing order of these hypotheses will be:

1. 75/2.5 dose vs placebo for HB(4%),
2. 37.5/2.5 dose vs placebo for HB(4%),
3. 75/2.5 dose vs placebo for AHI(4%),
4. 37.5/2.5 dose vs placebo for AHI(4%),
5. 75/2.5 dose vs placebo for ODI(4%),
6. 37.5/2.5 dose vs placebo for ODI(4%),
7. 37.5/2.5 dose vs 75/2.5 dose for HB(4%),
8. 37.5/2.5 dose vs 75/2.5 dose for AHI(4%), and
9. 37.5/2.5 dose vs 75/2.5 dose for ODI(4%).

All hypothesis tests will test that the two-sided p-value is less than 0.05.

All hypothesis tests for secondary endpoints will be reported using the nominal 0.05 two-sided alpha level.

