6.1. Primary Efficacy Analysis – HB(4%)

Multiple comparisons will be performed as described in Section 4.5. A repeated measures model (see Section 4.7) will be used to model change in $\log_{10}(\text{HB}[4\%] + 1)$ from baseline. Model based LS mean estimates will be provided for the following:

- mean change by study treatment (75/2.5 dose, 37.5/2.5 dose, placebo),

- difference in mean change between study treatments¹ (75/2.5 dose vs placebo, 37.5/2.5 dose vs placebo, and 75/2.5 dose vs 37.5/2.5 dose) with 95% confidence intervals and respective p-values (for null hypothesis).

If the model shows there is a visit (i.e., period) effect, then ad hoc analyses will be performed. A sensitivity analysis will be performed using the PP Set on the primary efficacy endpoint using the same methods described above and using HB(4%) with identity transform (i.e., without transform) on the mITT set.

Descriptive statistics for the reported value and change from baseline in $\log_{10}(\text{HB}[4\%] + 1)$ will be presented by study treatment. By taking the inverse transformations of the respective means, the geometric mean of HB(4%) + 1 and the ratio of the geometric mean to baseline will be reported.

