9. SAMPLE SIZE AND POWER CALCULATIONS

A total of 30 patients will enter the 3-treatment crossover study. The study will have 80% power to detect a treatment difference on the primary endpoint at a two-sided 0.05 significance level, if the true difference between treatments on HB is at least -3.7 % min/h. This assumes that the within-participant standard deviation is 9 and a discontinuation rate of less than 20%.

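### The SAP moves the primary endpoint from change in HB to change in log10(HB+1) without declaring it, and the stated 80% power does not describe the log-scale test

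*Protocol*

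**What the plan says.** **Protocol.** Section 3 lists the primary endpoint as "Change in Hypoxic Burden (HB) 4% (scored in reference to AHI 4%), 75/2.5 dose vs. placebo". No transformation is named. Section 8.1 says "A total of 30 patients will enter the 3-treatment crossover study" and claims 80% power at two-sided 0.05 for a difference of -3.7 %min/h, with a within-subject SD of 9 and less than 20% discontinuation. The protocol has no section describing the primary analysis model. Its amendment history records the move from AHI to HB as primary but mentions no transformation.

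**SAP.** The introduction says the plan is "based on the Protocol # APC-004 Version 2.0, dated 06 January 2021", which is the protocol version reviewed here. Section 2.2.1 makes the primary endpoint the change in log10 "of Hypoxic Burden (HB) 4% plus one (scored in reference to AHI[4%]), 75/2.5 dose vs. placebo". In Section 6.1, "A repeated measures model (see Section 4.7) will be used to model change in" log10(HB[4%]+1) from baseline. The same section assigns a sensitivity role to the analysis "using HB(4%) with identity transform (i.e., without transform) on the mITT set", and back-transforms the log results to geometric means of HB+1. Section 4.5 puts the 75/2.5 versus placebo comparison on HB(4%) first in the testing sequence and gives no scale. Section 9 repeats the protocol's power statement for the primary endpoint: 80% "if the true difference between treatments on HB is at least -3.7 % min/h", with a within-participant SD of 9.

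**The concern.** The two documents define the primary endpoint on different scales. A difference in mean HB is an absolute effect in %min/h. A difference in mean log10(HB+1) is, after back-transformation, a ratio of geometric means of HB+1. These are different estimands, and with about 24 completers their p-values need not fall on the same side of 0.05. The body of the SAP neither says that it departs from the protocol nor gives a reason.

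Three things follow:

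- A reader cannot see from the SAP when or why the scale was chosen.
- The testing sequence in SAP 4.5, read alone, does not say which HB test opens the gate.
- The only power claim in either document is in the units of what is now a sensitivity analysis, so the test that decides the primary hypothesis has no supported power.

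**Working it through.** **Inputs from the documents.** N = 30; 20% discontinuation leaves 30 × 0.8 = 24 completers; difference 3.7 %min/h; within-participant SD 9; two-sided 0.05, so z = 1.960; 80% power, so z = 0.842. Each participant receives both treatments. The baseline is common to a participant's periods, so it cancels from the paired contrast on either scale.

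**1. The plan's own figure, raw scale.** SE = SD × √(2/n); power = Φ(3.7/SE − 1.960).

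- n = 24: SE = 9 × √(2/24) = 2.598; 3.7/2.598 = 1.424; power = Φ(−0.536) = 30%.
- n = 30: SE = 9 × √(2/30) = 2.324; 3.7/2.324 = 1.592; power = Φ(−0.368) = 36%.
- If 9 is read as the SD of the paired difference, SE = 9/√n and power is 52% (n = 24) or 62% (n = 30).
- Noncentral t versions run one to three points lower: 28–29% and 34–35%, or 49–50% and 59–60%.

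A figure of about 80% appears only if the SD of the paired difference is 9/√2 = 6.36 with n = 24 (81%), or if 90 observations are counted as 90 patients (79%). The text supports neither. This is a separate defect. It matters here only because relabelling the existing statement as raw HB would not repair it.

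**2. Whether the raw inputs carry over to the log scale.** If a participant's HB on placebo is m and falls by 3.7, the log10 difference is log10((m − 3.7 + 1)/(m + 1)). The documents give no expected HB, so m is assumed. The log10 SD that gives 80% power with 24 completers is |difference| × √(24/2)/(1.960 + 0.842).

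| Assumed placebo HB | log10 difference | log10 SD for 80% power |
|---|---|---|
| 5 | −0.416 | 0.515 |
| 10 | −0.178 | 0.220 |
| 20 | −0.084 | 0.104 |

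The same 3.7 %min/h is a fivefold range of log10 effects (0.416/0.084 ≈ 5). The inputs do not carry over.

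**3. What log-scale power might be.** Power = Φ(|log10 ratio|/(SD × √(2/n)) − 1.960), with ratio and SD assumed. The range in each cell runs from n = 24 to n = 30.

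| Ratio of geometric means of HB+1 | SD 0.15 | SD 0.20 | SD 0.25 | SD 0.30 |
|---|---|---|---|---|
| 0.7 | 95–98% | 77–85% | 57–67% | 43–52% |
| 0.8 | 61–71% | 39–47% | 27–32% | 20–24% |

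**4. How often the two scales disagree (illustrative).** There were 20,000 simulated trials per scenario, with 24 completers and paired t-tests on HB and on log10(HB+1). HB was assumed log-normal, with median 10 or 20 %min/h, between-participant natural-log SD 0.7, within-participant natural-log SD 0.4 or 0.6, and true ratio 0.6 to 0.8.

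- The scales differed on p<0.05 in about 9% to 25% of trials.
- Significant on the log scale only: about 9% to 24%. Significant on the raw scale only: 0% to 3%. In every scenario at least four in five disagreements were log-only.
- Power was about 8 to 23 points higher on the log scale, for example 0.58 raw against 0.80 log (median 10, ratio 0.6, within SD 0.6).
- No trial was significant in opposite directions.
- At a true ratio of 1, rejection was about 5% on the log scale and 4% on the raw scale.

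**The case against.** An SAP may refine a protocol, and a log transform of a skewed, non-negative measure is a recognised choice. The SAP is internally clear on roles: 2.2.1 defines the log-scale endpoint and 6.1 labels untransformed HB as sensitivity, so both results will be reported with their status fixed in advance. All of this stands. The transform itself is not at fault.

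Four stronger readings are tempting, and the documents do not support them.

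- *Two rival primary tests.* The protocol names an endpoint and no test. That its endpoint is untransformed is inferred from the absence of a transformation and from the %min/h units in 8.1. The SAP specifies one primary model.
- *Raw HB has been abandoned.* It remains a pre-specified sensitivity analysis.
- *The two documents could yield opposite conclusions about the drug.* The simulated disagreements are mostly one scale reaching significance while the other falls short, and they show no type I inflation from using the log scale.
- *The scale was chosen after seeing results.* Nothing in the text suggests this. The text simply does not record the timing or the reason.

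The simulation also has limits. Log-normal data favour the log test by construction, and paired t-tests stand in for the SAP's three-treatment model. Several scenarios also imply more variability than the stated SD. A within-participant SD of 9 implies a paired-difference SD of 9 × √2 = 12.7, whereas the median-20 scenarios gave about 19 to 33.

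SAP Section 4 sends to the study report only changes not included in the SAP. A change made inside the SAP is therefore not caught by that sentence.

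**Conclusion.** The point holds as an undeclared change of primary scale together with a power statement that does not belong to the planned test. The scale mismatch and the units of the power claim can be read directly from Protocol 3 and 8.1 and SAP 2.2.1, 6.1 and 9, and rest on no assumption beyond reading the protocol's HB as untransformed.

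Power for the log-scale test cannot be computed from the documents. The 20% to 98% span in the working only shows how far it depends on the missing ratio and SD. The 9% to 25% disagreement rate is illustrative and depends on assumed log-normal HB; it measures a difference in power. The 80% also fails on the raw scale (28% to 36% as labelled, 49% to 62% if 9 is the SD of the paired difference), so the figure has to be recomputed on the decision scale.

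**What to change.** 1. Record in the SAP, dated before unblinding, that the primary scale differs from Protocol Section 3, and give the reason. A protocol amendment to Sections 3 and 8.1 would also do, but is not essential.
2. State in SAP 4.5 that the test on log10(HB[4%]+1) alone decides the HB steps of the sequence, with untransformed HB as sensitivity only.
3. Replace the power statement in SAP 9 with one on the log10 scale. Give the assumed ratio of geometric means of HB+1, the within-participant log10 SD and the source of both, and report whatever power 24 to 30 completers provide.

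The cost is a few sentences and one power calculation, which needs an SD estimate on the log10 scale. The analysis model and sample size need not change. The restated power may turn out below or above 80%.
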